## **9.0 DETAILS OF PROCEDURES**

### **9.1 Study Materials**

#### **9.1.1 Structured Clinical Interview for DSM-IV (SCID)**

The SCID-CT is a short semi-structured interview. With an administration time of approximately 15 minutes, it was designed to meet the need for a short but accurate structured psychiatric interview for multicenter clinical trials and epidemiology. The SCID-CT will be administered by raters at the study site. The SCID-CT must be administered by a site study staff member listed on the site delegation of authority log with at least 2 years of experience with the population under study. The results of this assessment will be used to confirm the diagnosis of schizophrenia or schizoaffective disorder and rule out any exclusionary diagnosis. The SCID will be administered at the screening visit.

#### **9.1.2 MATRICS Consensus Cognitive Battery (MCCB)**

The MCCB includes 10 tests that assess 7 cognitive domains: speed of processing, attention/vigilance, working memory, verbal learning, visual learning, reasoning and problem solving, and social cognition. The tests will be administered together in one 60-to 90-minute session. For subjects who use nicotine, the MCCB will be performed at least 30 minutes after nicotine intake. Though not strictly required by the protocol, whenever possible, the MCCB should be administered at the same time of day ( $\pm$  1 hour). The MCCB is a hybrid battery comprising multiple independently owned and published tests. Normative data for demographic corrections are derived from a single representative sample to which the tests were administered together as a unit, called "co-norming" [24]. The MCCB's high test-retest reliability makes it a sensitive and accurate measure of cognitive change, and its minimal practice effects ensure that it is appropriate for repeat testing [25]. The MCCB was developed by the National Institute of Mental Health (NIMH) MATRICS initiative. The MATRICS was designed to stimulate the development of psychopharmacological agents to improve cognition in schizophrenia. The selection of tests included in the MCCB involved a broad-based interdisciplinary consensus process that is described in more detail on the MATRICS website ([www.matrics.ucla.edu](http://www.matrics.ucla.edu)). Details of administration are included in the study-specific MCCB manual. The MCCB will be administered at baseline and end of study.

#### **9.1.3 Positive and Negative Syndrome Scale (PANSS)**

The PANSS is an interview-based measure of the severity of psychopathology in adults with psychotic disorders. The measure is comprised of 30 items and 3 scales: the Positive scale assesses hallucinations, delusions, and related symptoms; the Negative scale assesses emotional withdrawal, lack of motivation, and similar symptoms; and the General Psychopathology scale addresses other symptoms such as anxiety, somatic concern, and disorientation. An anchored Likert scale from 1-7, where values of 2 and above indicate the presence of progressively more severe symptoms, is used to score each item. Individual items are then summed to determine scores for the 3 scales, as well as a total score. A Composite scale score (Positive scale score - Negative scale score) can also be calculated to show the relative valence of positive and negative symptoms. Total time required for the PANSS interview and scoring is approximately 30-40 minutes. PANSS raters will be required to meet specific training and education criteria before they are certified to rate for this study. In addition, raters will receive specific training and education regarding all the following assessments prior to study initiation. The PANSS will be administered at baseline, week 6, and end of study.

#### **9.1.4 fMRI Procedures**

MRIs will be performed on all subjects that meet criteria for scanning (i.e. those that will fit in the scanner and do not have metal in their body). Scanning will be performed on a 3.0T Siemens TIM Trio MRI scanner with a UNIX based host computer (Sun Microsystems), actively shielded gradients, and echo-planar capability. Positioning calipers are used to fixate the head and reduce patient motion during the study. Once the MR technician and research personnel have position the subject comfortably in the scanner, the subject is then monitored with a wide angle and a telephoto camera. An auditory system provides two-way communication making it easier to explain the task to the subject. A slim line headphone set is used for maximum patient comfort. Visual stimuli are delivered to a custom rear projection screen placed inside the bore of the magnet approximately 24" from the subject. The subject views the stimuli via a mirror attached to the head coil that can be adjusted easily.

*Structural imaging*

1. T2 structural images: A series of T2-weighted images will be acquired for clinical neuroradiological examination and review for incidental findings.
2. T1 structural images: A series of T1-weighted images will be acquired to provide high resolution anatomic images of the brain for morphometric analysis and for aligning functional images for averaging data across subjects.

*Functional imaging*

Functional images will be acquired using echo-planar imaging. Acquisition parameters will be optimized according to task completed. Tasks will be performed for 8-12 minutes depending on the behavioral paradigm. Pauses are provided between tasks to allow subjects to rest and for providing instructions. Manual button press responses will be record using an MR compatible button box.

3. IAPS Decision-Making Task: For this task each subject is presented with a series of picture sets from the International Affective Picture System that present either positive, negative, or neutral stimuli. Participants will be asked to specifically quantify positive and negative preferences involving (i) decision-making regarding the valence of behavior, and (ii) judgments that determine the magnitude of reward valuation and aversion.
4. "Spinner" Monetary Game of Chance Task: For this task, a \$50 endowment is provided, and the subjects were told that during the game, they might lose some or all of this stake, retain it, or increase it. They are presented one of three spinners, which are subdivided into three equal sectors—each labeled with a different monetary value. The image of an arrow rotates around the center of the spinner during the prospect phase, and then stops at one sector at the start of the "outcome" phase. The amount of money indicated on that sector would be added to or subtracted from the subject's total, but the cumulative winnings or losses are not displayed. The timing of the prospect and outcome phases made it possible to distinguish hemodynamic signals associated with anticipation from those associated with the experience of outcomes. During control trials, the display consists of a stationary fixation point. The design is in a single-trial format, and the trial sequence will be counter-balanced.

5.

Capacity Working Memory Task: This task is a spatial variant of the Sternberg Item Recognition paradigm, a paradigm which field experts have identified as promising for imaging biomarkers in clinical trials evaluating effects on working memory. During a brief encoding phase, subjects view an array of containing a variable number of items (3,5, or 7 items). They are to remember the location of items over a delay period of variable duration (2,4, or 6 sec) and then respond during response phase whether the presented probe appears in the location of one of the items presented in the array. Activation in the DLPCF and related regions during the delay period of correctly performed trials will be evaluated.

6. Resting State: During this task subjects will be asked to keep their eyes open and fixate a central crosshair.

fMRI task order will be pseudo randomized across groups to account for order effects. Start and stop time of the scan session will be recorded. MRI procedures take up to 2 hours to complete.

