Additionally, this study will evaluate the potential WM enhancing and NS reduction effects of MMFS-202-302 among a group of individuals with schizophrenia disorder on a series of functional magnetic resonance imaging (fMRI) WM and reward tasks. We will evaluate whether MMFS-202-302 + APD vs. placebo + APD increases cognitive performance on a task of WM, and associated task-related increases in BOLD activation in the dorsolateral prefrontal cortex (DLPFC), and posterior parietal cortex (PPC). Additionally, we will assess whether MMFS-202-302 + APD vs. placebo + APD enhances reward circuitry (orbitomedial prefrontal cortex [OMPFC], anterior cingulate [ACC], nucleus accumbens [NAc], and ventral tegmental area [VTA]) and reward behaviors in the expression of NS. Positive findings will provide biomarker evidence for MMFS-202-302 effects on neural systems underlying these cognitive processes.

Finally, this study will measure brain network interactivity using electroencephalography (EEG) at baseline and end of study to examine any differences in activation or connectivity using learning and memory tests over the course of the trial. More information can be found in sections 5.0, 7.4, and 8.1 below.

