### 2.1 STUDY OBJECTIVES

1. To determine the effectiveness of 9 weeks' supplementation with MMFS-202-302 as augmentation of atypical antipsychotic medication, to improve working memory or other specific domains of cognitive function, e.g. attention, executive function, declarative memory, etc., in patients with schizophrenia or schizoaffective disorder. The primary outcome measure will be a main effect of group on the 9-wk-change-from-baseline working memory subscale of the MATRICS Cognitive Consensus Battery (MCCB). The MCCB consists of 10 cognitive tests covering seven domains. This will be augmented by additional neuropsychological measures of verbal fluency (FAS Phonemic Fluency), working memory (Brown-Peterson's Auditory Consonant Trigrams) and executive function (the Wisconsin Card Sorting Test). The MCCB composite score, and each of the additional cognitive domain subscales listed above will be secondary outcome measures.
2. To determine the effect of MMFS-202-302 on global function, as measured by the Clinical

Global Impressions Scale (CGI) assessment of change (CGI-C).

3. To determine the effect of MMFS-202-302 on negative symptoms of schizophrenia, as measured by the Brief Negative Symptom Scale (BNSS) and PANSS negative subscale, and imaging of brain reward networks (OMPFC, ACC, NAc, VTA).
4. To determine the effect of MMFS-202-302 on positive symptoms of schizophrenia, as measured by the PANSS positive subscale.
5. To determine the effect of MMFS-202-302 as augmentation of atypical antipsychotic medication on both the behavioral performance and activation patterns in schizophrenia patients during a WM neuroimaging paradigm. Specifically, investigation in whether improvement from baseline task performance occurs for the MMFS-202-302 + APD group, and if this improvement is associated with increases in WM-related brain region activation (DLPFC & PPC).
6. To evaluate whether MMFS-202-302 results in greater functional connectivity within identified reward and working memory circuits in subjects with schizophrenia.
7. To determine whether MMFS-202-302 stimulates an overall enhancement or restoration of typical structural brain abnormalities in schizophrenia, as measured by cortical volume and thickness of the neocortex.
8. To examine the effect of MMFS-202-302 on neural connectivity and activation in EEG assessment, using measurements of learning and memory.

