### **8.3 Analysis of Functional Imaging Data**

Mixed effects models and analysis of variance will be used to evaluate behavioral performance on tasks administered in the scanner to characterize working memory performance and reward valuation across task conditions and to contrast performance between MMFS-202-302 vs. placebo treated groups. Event-related fMRI analyses will be carried out using SPM v8.0 (Statistical Parametric Mapping version 8.0 <http://www.fil.ion.ucl.ac.uk/spm/software/spm8/>) in a MATLAB environment. A fixed effect analysis will be used to model activation associated during events of interest in each subjects' time series data. Activation maps from these analyses will be carried forward to higher-level mixed effects analyses to model each group's activation during the events of interest allowing for separate estimations of variances for each group. Analyses contrasting activation in the MMFS-202-302 vs. placebo groups will include both whole brain and a priori regions of interest (i.e., DLPFC, PPC, OMPFC, ACC, NAc).

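### Working-memory activation is specified on correctly answered trials; if the drug changes accuracy, the arm contrast is no longer a clean randomised comparison and needs a load-balanced, all-delay contrast beside it

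*Combined protocol and SAP*

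**What the plan says.** Section 9.1.4 describes a spatial item-recognition task with arrays of 3, 5 or 7 items and a delay of 2, 4 or 6 seconds. The patient must "respond during response phase whether the presented probe appears in the location of one of the items presented in the array". The activation measure is then stated: "Activation in the DLPCF and related regions during the delay period of correctly performed trials will be evaluated".

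Objective 5 in Section 2.1 asks "whether improvement from baseline task performance occurs for the MMFS-202-302 + APD group", and then "if this improvement is associated with increases in WM-related brain region activation". Section 1.1.3 puts the same hypothesis as a drug-placebo comparison: the drug "increases cognitive performance on a task of WM, and associated task-related increases in BOLD activation in the dorsolateral prefrontal cortex" and in posterior parietal cortex. It adds that positive findings would count as biomarker evidence.

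Section 8.3 gives the analysis. At the first level, "A fixed effect analysis will be used to model activation associated during events of interest"; those events are not defined. At the group level, "Analyses contrasting activation in the MMFS-202-302 vs. placebo groups will include both whole brain and a priori regions of interest". In-scanner task performance is analysed separately, across task conditions and between arms.

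No section describes an all-trial contrast, a regressor for error trials, activation modelled by load, or a sensitivity analysis for the choice of trials. Working-memory activation is not among the primary, secondary or tertiary/exploratory endpoints in Section 3.0.

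**The concern.** Randomisation balances the patients. It does not balance the trials that each patient answers correctly once on treatment. If the drug raises accuracy, as Objective 5 hopes, the drug arm's correct set at follow-up will tend to hold more high-load trials and a smaller share of lucky guesses than the placebo set. The contrast then compares somewhat different kinds of trial. It also leaves out the failed trials, which are the ones that a drug improving maintenance would convert.

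At stake is the reading of the DLPFC and PPC result. A small correct-trial difference could understate a real effect on delay activity, and a modest positive one could partly reflect a change in load mix. Neither could be read, on its own, as the randomised effect of the drug on delay activity.

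**Working it through.** **The plan's own figures.** The documents give no sample size, effect size or power for activation. The only design figures, in Section 8.1, concern the MCCB working-memory score: 28 per group, and 74-83% power. They reproduce. With a difference of 5, SD 6.5 and two-sided alpha 0.05, the t-based calculation gives 27.5, rounded up to 28, with power of 74.2% at 24 and 83.4% at 30 per group. They do not bear on this point.

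**Inputs.** From the documents: the correct-trial rule, loads of 3, 5 and 7, and a yes/no response. Every probability and activation value below is an assumption. Activation is in arbitrary units that do not convert to a between-patient effect. The arms are taken as balanced at baseline.

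**1. Guessing, single load.** A trial is maintained with probability p (activation 1). Otherwise activation is 0 and the answer is a guess, correct with probability g.

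- Accuracy: a = p + (1 − p)g.
- Mean activation: p on all trials, p/a on correct trials.
- All-trial arm difference: p1 − p0.
- Correct-trial arm difference: p1/a1 − p0/a0 = g(p1 − p0)/(a0·a1).
- Fraction kept: g/(a0·a1).

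With g = 0.5:

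| p0 to p1 | accuracy | all trials | correct trials | kept |
|---|---|---|---|---|
| 0.30 to 0.60 | 0.65 to 0.80 | 0.300 | 0.288 | 0.96 |
| 0.50 to 0.65 | 0.75 to 0.825 | 0.150 | 0.121 | 0.81 |
| 0.60 to 0.75 | 0.80 to 0.875 | 0.150 | 0.107 | 0.71 |
| 0.70 to 0.85 | 0.85 to 0.925 | 0.150 | 0.095 | 0.64 |
| 0.80 to 0.90 | 0.90 to 0.95 | 0.100 | 0.058 | 0.585 |

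The ratio passes 1 when accuracy is low: for p from 0.3 to 0.5 it is 0.5/(0.65 × 0.75) = 1.03. It also depends heavily on g. For p from 0.60 to 0.75 it is 0.25/(0.70 × 0.8125) = 0.44 at g = 0.25, and 0 at g = 0.

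**2. Load mix alone.** Let activation depend on load only (1, 1.5, 2) and be untouched by the drug, so the true difference is 0. Let maintenance at the three loads be 0.90/0.60/0.30 on placebo and 0.93/0.75/0.50 on drug, with g = 0.5. Accuracy is then 0.95/0.80/0.65 and 0.965/0.875/0.75. Pooling correct trials over loads:

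- Placebo: (0.95 + 1.20 + 1.30)/2.40 = 1.4375.
- Drug: (0.965 + 1.3125 + 1.50)/2.59 = 1.4585.
- Spurious difference: +0.021. Averaging within load returns 0.

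**3. Load and maintenance together.** Same values, with activation 1, 1.5 or 2 on maintained trials and 0 otherwise:

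- All trials, loads equal: 3.055/3 − 2.400/3 = 0.218.
- Correct trials pooled: 3.055/2.59 − 2.400/2.40 = 0.180 (82% kept).
- Correct trials within load, then averaged: 1.194 − 0.998 = 0.196 (90% kept).

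**4. Better retrieval, unchanged delay activity.** Let delay signal x be standard normal and P(correct) = Φ(b + 0.5x), with the drug raising b by 0.4. With z = b/√1.25, accuracy is Φ(z) and mean x on correct trials is 0.447·φ(z)/Φ(z).

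- b from 0.4 to 0.8: accuracy 0.640 to 0.763; mean x 0.262 to 0.181, a shift of −0.081 trial-SD.
- b from 0.8 to 1.2: accuracy 0.763 to 0.858; mean x 0.181 to 0.117, a shift of −0.064.

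Cases 2 and 4 have opposite signs, so the direction is not fixed.

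**The case against.** The strongest reply is that correct-trial activation is a legitimate target: it asks whether delay activity differs given successful performance. The accuracy effect is not lost, since Section 8.3 analyses task performance by condition and by arm. This stands, and it is why the correct-trial contrast should be kept.

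An all-trial contrast also has its own weakness. In the two-state model, all-trial activation is p and accuracy at g = 0.5 is (1 + p)/2, so one is an exact linear function of the other. Correct-trial activation, 2p/(1 + p), responds to p less steeply once p exceeds about 0.41. Using all-trial activation alone would make the performance-activation link in Objective 5 more mechanical. This also stands: the all-trial contrast belongs beside the correct-trial one and should not replace it.

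Three stronger readings are tempting, and the documents do not support them:

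- A reader might infer that all other trials are excluded. Section 9.1.4 does not say so, and the events of interest in Section 8.3 are undefined. What can be said is that no other trial set is named.
- A reader might infer that the rule necessarily hides a drug effect. The sets differ systematically only if accuracy differs by arm, and the shift can go either way. If the drug changes neither accuracy nor activation, the correct-trial contrast is unbiased. In the two-state model with some guessing it never reverses sign.
- A reader might take the percentages as estimates for this trial. No section gives accuracy, the share of matching probes or activation values, so even the 50% guess rate is assumed.

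**Conclusion.** The point holds in a limited form. The only trial set named for working-memory activation is selected by an outcome that the drug is hypothesised to change, and nothing in Section 8.3 balances load or supplies another contrast. If accuracy differs by arm, the correct-trial contrast alone cannot be read as the randomised effect on delay activity.

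The size is unknown. With assumed 50% guessing, roughly 60% to 95% of the all-trial difference is kept over the values tabulated. Load mix alone adds about +0.02 units in one assumed case, and improved retrieval shifts the contrast by −0.06 to −0.08 trial-SD in another. All of these rest on invented trial-level inputs and show what is possible, not what to expect.

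The MCCB primary endpoint, the sample size and alpha are untouched. This is a minor improvement to one imaging objective, to which only scannable patients contribute.

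**What to change.** In Sections 9.1.4 and 8.3, before unblinding:

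- Define the events of interest for this task.
- Keep the correct-trial contrast, but estimate it within each load (3, 5, 7) and average the three loads with equal weight.
- Add a drug-placebo contrast on all delay periods, with one all-delay regressor per load and loads weighted equally in each patient and session. Report it beside the correct-trial contrast as the total randomised effect on delay activity.
- Report accuracy by arm and load next to both.
- State that the correct-trial contrast is conditional on successful performance.

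A single all-delay regressor per load is preferable to separate incorrect-trial regressors, which would often be empty. Section 9.1.4 gives tasks of 8-12 minutes. Assuming 12-20 seconds per trial, that is 24-60 trials, or 8-20 per load. At an assumed 95% accuracy for 3 items, the chance of no error at that load in a session is 0.95^20 = 36% to 0.95^8 = 66%.

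The cost is one extra first-level model and one extra contrast, with no new scans or visits. The downside is that the all-trial estimate includes lapsed trials and so tracks accuracy, which should be said when it is reported.

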#### **9.1.5 Brief Negative Symptom Scale**

The Brief Negative Symptom Scale (BNSS): [26] was developed in response to the consensus conference and the NIMH MATRICS initiative on negative symptoms. It includes assessment of the 5 domains included in the Consensus Development Conference: blunted affect, alogia, asociality, avolition and multiple aspects of anhedonia (e.g., anticipatory pleasure and frequency of pleasurable activities). It has demonstrated strong inter-rater reliability, internal consistency, stability, and convergent/discriminant validity [27, 28]. The BNSS yields subscale scores for each domain, as well as a total global score.

#### **9.1.6 Clinical Global Impressions Scale (CGI)**

The Clinical Global Impressions (CGI) Severity and Change Scale will be used for repeated evaluations of global psychopathology. The CGI scale is widely used in schizophrenia research. The CGI-S is a single Likert scale rating severity of psychopathology on a scale of 1 (normal, not ill) to 7 (very severely ill). The CGI-C is a single Likert scale rating change of psychopathology during the trial on a scale of 1

C

(very much improved) to 7 (very much worse). The CGI will be completed at baseline and end of study.

### **9.1.7 Calgary Depression Scale for Schizophrenia**

CDSS: The CDSS is a clinician-administered psychiatric symptom rating scale intended to measure the level, duration, and frequency of depressive symptoms in patients diagnosed with schizophrenia or schizoaffective disorder. The CDSS, developed at the University of Calgary [29], has good construct validity, internal reliability, and interrater reliability. The type and level of depression measured by this scale is also reported to have divergent validity from symptoms associated with schizophrenia and schizoaffective disorder. Clinicians administering this scale ask patients about their depressive symptoms since the last study visit. Each of the 9 items of the CDSS is scored between 0 (absent) and 3 (severe). The 9 items are then added together to yield a single total score in the range of 0 to 27. A score of 7 or higher is considered to be 85% sensitive to a diagnosis of major depressive disorder. For study eligibility, a CDSS score of  $\leq 10$  (minimal level of depression) will be required. The CDSS is used in this study as both a screening assessment and a safety assessment for depressive symptoms. The CDSS will be performed at baseline, and the final study visit.

